#### 15.4.1.2 Change from baseline to Month 6 in UACR

The ANCOVA after MI assuming MAR described in Section 15.3.3 will be used to analyze the change from baseline to Month 6 on the mFAS, on original values at baseline, Month 1, Month 3, Month 5, and Month 6.

Subjects with the baseline UACR value missing will be excluded from this analysis.

## 15.4.2 Echocardiography-based endpoints

An ANCOVA model will be used to analyze the change from baseline to Month 6 of each echocardiography parameter on the mFAS. The following terms will be included in the model: baseline value, the two stratification factors (sex and ERT treatment status at screening), and the treatment group.

The estimate and the two-sided 95% CI will be calculated for the difference in the mean change from baseline to Month 6 between lucerastat and placebo.

This analysis will be implemented by the following SAS® code:

```
proc mixed;  
  class sex ertstatus treatment;  
  model chg = sex ertstatus bsl treatment;  
  lsmeans treatment / cl pdiff;  
run;
```

The analysis described above will be repeated on log-transformed values leading via the back-transformation  $x \rightarrow (e^x - 1) \times 100$  to treatment group results expressed as percent change from baseline and treatment effect estimate expressed as percent change relatively to placebo.

## 15.4.3 Pain medication endpoints based on daily entries in eDiary

### 15.4.3.1 Subject mean weekly dose of opioid analgesics from baseline up to Month 6

The same approach (ANCOVA) as described in Section 15.4.2 will be used to analyze the overall mean weekly dose of opioid analgesics from baseline to Month 6 on the mFAS.

### 15.4.3.2 Use of significant rescue pain therapy from baseline up to Month 6

The same approach (CMH test) as described in Section 15.2.5.1 will be used to analyze this endpoint on the mFAS.

### 15.4.3.3 Total number of days on significant rescue pain therapy from baseline up to Month 6

Due to the expected distribution of this endpoint (count data) and the varying observation times per subject, this endpoint will be analyzed by determining the annualized rate of days on significant rescue pain therapy using a negative binomial regression model adjusted for the stratification factors.

The observation time (in years; defined in Section 9.5.3) will be used as an offset variable in the model in order to account for varying lengths of the observation period for each subject.

The treatment effect will be expressed as a rate ratio between lucerastat and placebo and will be presented with its 95% CI.

Since days with missing eDiary entries are excluded from the calculations (not imputed), the ARRT is unbiased in the presence of missing data as long as the unobserved rate of days with significant rescue pain therapy over the missing entries is the same as that observed over the non-missing entries. This assumption is considered reasonable given that measures have been put in place to minimize the risk of missing data [see protocol section 7.2.2.2.4].

This analysis will be implemented by the following SAS® code:

```
proc genmod;
  class sex ertstatus treatment;

  model nbdays = sex ertstatus treatment / dist=negbin link=log offset=ltime;
  * ltime = log(observation time);
  lsmeans treatment / cl exp;
  estimate "lucerastat - placebo" treatment 1 -1;
run;
```

#### 15.4.4 Clinical symptoms endpoints based on data collected at site visits

##### 15.4.4.1 *Change from baseline to Month 6 in the subject's rating of item 5 score of the BPI-SF ("pain on the average in the last 24 hours")*

The same approach (ANCOVA) as described in Section 15.4.2 will be used to analyze this endpoint on the mFAS. The same approach will also be used on the log-transformed data, leading (via the back transformation  $x - > (e^x - 1) \times 100$ ) to treatment group results expressed as percent change from baseline and treatment effect estimate expressed as percent change relatively to placebo.

##### 15.4.4.2 *Change from baseline to Month 6 in the total score of the subject's rating of item 9 of the BPI-SF*

The same approach (ANCOVA) as described in Section 15.4.2 will be used to analyze this endpoint on the mFAS.

##### 15.4.4.3 *Change from baseline to Month 6 in the subject's rating of neuropathic pain severity as measured by the PGIS-P*

The same approach (CMH test) as described in Section 15.2.5.1 will be used to analyze on the mFAS the proportion of subjects experiencing improvement.

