10.5 Sample size

The planned sample size for this study is 99 subjects using a 2:1 allocation ratio (66 lucerastat, 33 placebo) and is primarily based on a test for the mean difference between lucerastat and placebo in the change from baseline to Month 6 in the “modified” BPI-SF3 score.

The sample size calculation for the primary endpoint analysis is based on the following assumptions: a clinically relevant difference of 2 points on the 11-point scale (0–10) between lucerastat and placebo, a corresponding SD of 3 points, a two-sided type I error of 5%, and equal group variances. These assumptions come from an expected mean decrease from baseline to Month 6 in BPI-SF3 in the lucerastat group of 1.0-1.5 (2-year data for subjects on ERT; [Hoffmann 2007b]), and an expected mean increase from baseline in the placebo group of approximately 0.5 to 1.0 [Weidemann 2014]. Following these assumptions 99 subjects will provide a power of 87.2% to detect a treatment difference between lucerastat and placebo on the primary endpoint. The calculations were conducted using East 6.5 based on a two-sided t-test for independent samples.

For the analysis of the secondary efficacy endpoints, it is expected that about 70% of the randomized subjects will be included in the mFAS-GIS. Under this assumption the assessment of the secondary endpoints may be carried out on about 69 subjects (approximately 46 on lucerastat and 23 on placebo). Little is known from the literature on the expected effect size that might be observed for these endpoints however a reasonable treatment effect on the abdominal pain endpoint (NRS-11) could be a difference (delta) of

1.5–2.5 points on that scale with an expected variability (SD) in the region of 2.5–3.5. For illustration purposes, and in absence of missing data, the power to detect such an effect with this sample size for the analysis of a continuous endpoint is shown in [Table 7](#).

Table 7 Power to detect a treatment difference for continuous secondary endpoints analyzed on the mFAS-GIS for a range of deltas and SDs (n = 69 subjects)

alpha = 5% two-sided			
delta	SD = 2.5	SD = 3.0	SD = 3.5
1.5	63.9%	48.8%	38.0%
2.0	87.0%	73.0%	59.7%
2.5	97.1%	89.5%	78.7%

SD = standard deviation.

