### **9.6.3 Change from baseline to Month 6 in the subject's rating of severity of neuropathic pain as measured by the PGIS-P**

The change in severity of neuropathic pain from baseline to Month 6 will be calculated as the PGIS-P value observed at Month 6 minus the baseline value.

Subjects with a negative change from baseline (change in PGIS-P < 0) will be considered as “improvement”, while a change  $\geq 0$  will be considered as “no improvement”.

The values collected during the study will be mapped to protocol visits according to the windowed times described in [Table 5](#).

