##### 15.4.4.4 *Subject rating of change in neuropathic pain severity since study treatment start as measured by the PGIC-PS at Month 6*

The same approach (CMH test) as described in Section 15.2.5.1 will be used to analyze on the mFAS each of the 3 response variables defined in Section 9.6.4.

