**15.4.4.6 Subject rating of change in disease severity since study treatment start as measured by the PGIC-DS at Month 6**

The same approach (CMH test) as described in Section 15.2.5.1 will be used to analyze on the mFAS each of the 3 response variables defined in Section 9.6.6.

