**15.4.4.7 Change from baseline to Month 6 in the total score of the subject's rating of the CESD-R-20**

The same approach (ANCOVA) as described in Section 15.4.2 will be used to analyze this endpoint on the mFAS.

The change from baseline to Month 6 in risk of depression will be compared between treatment groups using the CMH test stratified by sex and ERT treatment status at screening (treated vs not treated) at the two-sided significance level of  $\alpha = 0.05$ .

Due to the ordinal nature of the change in risk, modified ridit scores will be used to obtain the Van Elteren extension of the Wilcoxon rank-sum test. This analysis will be implemented by the following SAS® code:

```
proc freq;  
  tables sex*ertstatus*treatment*riskchange / nocol nopercnt scores=modridit cmh2;  
run;
```

The change from baseline to Month 6 in risk of depression will be further detailed within each treatment group by a shift table of the 5-level classification.

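### No between-arm test of PGIS-P, PGIS-D, PGIC-PS or PGIC-DS uses the full ordinal scale or separates worsening from no change, which costs power on these supportive endpoints

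*SAP*

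**What the plan says.** Protocol 6.1.4.4 lists change from baseline to Month 6 in PGIS-P and PGIS-D, and the PGIC-PS and PGIC-DS ratings at Month 6, among the other efficacy endpoints. PGIS has 4 ordered levels, so its change runs from -3 to +3. PGIC has 7 ordered levels (Protocol 7.2.2.4 and 7.2.2.5).

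**PGIS.** SAP 9.6.3 makes the change binary: "Subjects with a negative change from baseline (change in PGIS-P < 0) will be considered as" improved, and a change of 0 or more is not improved. SAP 9.6.5 does the same for PGIS-D. In 15.4.4.3 the stratified CMH method "will be used to analyze on the mFAS the proportion of subjects experiencing improvement", and 15.4.4.5 repeats this for PGIS-D.

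**PGIC.** SAP 9.6.4 and 9.6.6 define three yes/no variables: levels 1–3, levels 1–2, and level 1. The CMH method "will be used to analyze on the mFAS each of the 3 response variables defined in Section 9.6.4" for PGIC-PS (15.4.4.4), and "will be used to analyze on the mFAS each of the 3 response variables defined in Section 9.6.6" for PGIC-DS (15.4.4.6).

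**Another ordinal outcome.** For change in depression risk (decreased, unchanged, increased), SAP 15.4.4.7 cites the ordinal nature of the variable and says that "modified ridit scores will be used to obtain the Van Elteren extension of the Wilcoxon rank-sum test".

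**The concern.** PGIS-P and PGIC-PS are the patient-global ratings that sit beside the primary pain result. As planned, unchanged and every grade of worse are one category in every test. For PGIS, an improvement of one category also counts the same as one of three. A lucerastat benefit that shows partly as less worsening, or as larger rather than more frequent improvement, is invisible to the PGIS tests. The PGIC cuts see the size of improvement but not the avoidance of worsening, and they give three overlapping p-values per scale with none named as the main one.

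The SAP treats a three-level outcome as ordinal in 15.4.4.7 but does not do so for two richer scales, and gives no reason. What is at stake is the chance that the supportive ratings miss a real effect. The validity of the primary test is not affected.

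**Working it through.** **1. The plan's own figure.** Protocol 10.5 assumes a 2-point difference, "a corresponding SD of 3 points, a two-sided type I error of 5%, and equal group variances", and 66 versus 33 subjects. The standard error is 3 × √(1/66 + 1/33) = 0.640, so the noncentrality is 2/0.640 = 3.13 on 97 degrees of freedom. Two-sided t-test power is 87.2%, as stated. No power is stated for PGIS or PGIC, so everything below rests on assumed category distributions.

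**2. One PGIS case by hand (66/33).** Order the change as two or more better, one better, unchanged, one worse, two or more worse. Assume placebo 5/20/55/17/3% and a latent normal shift of 0.5 SD. Lucerastat becomes 12.6/30.5/47.9/8.1/0.9%.

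- Binary test: improved 43.1% versus 25.0%, difference 0.181. The pooled rate is 0.371, so SE under the null is √(0.371 × 0.629 × (1/66 + 1/33)) = 0.103. SE under the alternative is √(0.431 × 0.569/66 + 0.25 × 0.75/33) = 0.097. Power ≈ Φ((0.181 − 1.96 × 0.103)/0.097) ≈ 42%.
- Rank test: P(lucerastat better) + ½P(tie) = 0.447 + 0.172 = 0.619, which is 0.119 above ½. The pooled category proportions have Σq³ = 0.149, so SE ≈ √(100/(12 × 66 × 33) × (1 − 0.149)) = 0.057. Power ≈ Φ(0.119/0.057 − 1.96) ≈ 55%.

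Simulation of the same case gives 42% and 56%, a loss of about 14 points.

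**3. Other assumed PGIS distributions** (simulated, 66/33, shift 0.5 SD; losses taken before rounding; four-category lists merge the worse grades):

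| Placebo distribution (%) | Rank test | Binary test | Loss (points) |
|---|---|---|---|
| 10/30/57/3 | 54% | 48% | 6 |
| 5/25/60/10 | 54% | 45% | 8–9 |
| 5/20/55/17/3 | 56% | 42% | 14 |
| 3/12/55/25/5 | 57% | 35% | 21 |

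With shifts from 0.4 to 0.667 SD and both 66/33 and 79/39 (the SAP section 2 numbers), these cases lose about 4 to 24 points.

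**4. The plan's own pain means, cut into five categories.** Placebo +0.5 to +1.0, lucerastat −1.5 to −1.0, SD 3, with assumed cuts at ±c and ±2.5c for c from 1.0 to 2.5 points (66/33). At c = 1.5 and means +0.75/−1.25, power is 83.7% for the rank test and 65.8% for the binary test, a loss of 17.9 points. Over the grid the loss runs from 12.9 to 24.8 points. Steps 3 and 4 together give roughly 4 to 25.

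**5. PGIC-PS.** With placebo 5/10/20/40/15/8/2%, shift 0.5 SD and 79/39, the rank test has 67% power. The three cuts, from most to least lenient, have 52%, 40% and 21%. Over all cases run, the most lenient cut loses about 9 to 20 points and the middle cut about 15 to 40.

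**6. With stratification.** Steps 2 to 5 are unstratified and assume no missing ratings. A separate simulation used the four strata and mapped BPI-SF3 to ratings. It assumed PGIS cut-points at 1/4/7, PGIC cut-points at changes of 0.75/2.5/5, baseline mean 6.3 (SD 1.5) and rating noise SD 0.5–1.0. At 66/33, PGIS power was 53–60% (CMH) versus 61–68% (Van Elteren), and PGIC-PS power was 57–64% (best single cut) versus 71–77%. Type I error of the full-scale tests was 4.4–5.3%.

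**7. Does it depend on placebo worsening?** Under a mapping of the step 6 kind, unstratified at 66/33, the PGIS loss was about 9–11 points with the plan's means and about 7–11 when placebo improves. In step 3 the loss is smallest where 40% of placebo subjects improve and only 3% worsen, but it does not vanish. The size varies with the mix; the loss itself does not need placebo to worsen.

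**The case against.** Several points on the other side stand.

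- These endpoints are outside the fixed sequence (SAP 15.1), no power is claimed for them, and Protocol 10.3.4 leaves their analysis to the SAP.
- Worsening of pain is compared between arms elsewhere: the primary ANCOVA, the MMRM, the eCDF plots by arm, and the ANCOVAs of BPI-SF items 5 and 9. The general rule in SAP 14 would also tabulate the rating categories by arm.
- PGIC is not a single split. It has three graded cuts, and Protocol 6.6.1 gives partial support for the middle one by linking a 30% pain reduction to the top two PGIC categories. The same PGIC and PGIS splits serve as anchors in SAP 15.2.5.8 and 15.2.5.9, so test and anchor definitions agree.
- The CMH analysis yields a matching odds ratio and risk difference with CIs. A rank test does not, as SAP 15.3.2 says of its own rank ANCOVA.

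These limit severity and are good reasons to keep the proportions. They do not supply the missing test. None of the three PGIC cuts separates worse from unchanged, and the full-category anchor plots pool the two arms.

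**Conclusion.** The point holds in a limited form. The four scales have no between-arm test on the ordinal scale, and power is lost through ordinary dichotomisation: roughly 4 to 25 points for PGIS-P, and 9 to 20 for PGIC-PS at its most favourable cut. The direction was the same in every scenario run. The size depends on category distributions that the documents do not give.

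Three stronger readings are not supported:

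- A reader might infer one fixed loss for all four scales. The documents give no rates from which to derive one. The disease ratings also cover abdominal pain, diarrhea and constipation, so PGIS-D and PGIC-DS cannot be read off a pain model and were not modelled.
- A reader might tie the loss to "an expected mean increase from baseline in the placebo group of approximately 0.5 to 1.0" in Protocol 10.5. It arises without that assumption, and Protocol 3.2 itself describes a general tendency to improve irrespective of allocation.
- A reader might conclude that the primary result or the type I error is at risk. Neither is.

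This is a worthwhile, low-cost improvement to supportive endpoints.

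**What to change.** In SAP 15.4.4.3 to 15.4.4.6, name one between-arm test per scale: the stratified Van Elteren test on the ordinal value (PGIS change −3 to +3; PGIC 1 to 7). Reuse the 15.4.4.7 code with the rating in place of the risk change. For PGIS, the 15.3.2 rank ANCOVA with baseline PGIS as covariate is an alternative. Choose one before unblinding. Keep the improvement proportions and the three PGIC cuts, with their odds ratios, risk differences and CIs, as the clinically readable effect estimates.

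Also state one missing-rating rule. SAP 15.2.5.1 counts missing as non-response, as the worst outcome, while 9.6.4 speaks of observed Month 6 data. The rule should be no more favourable than 15.2.5.1: for example worst rank, with an observed-data analysis as sensitivity. Giving a missing rating a change of 0, or PGIC level 4, should be avoided, because a missing subject would then outrank one who worsened.

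The cost is SAP wording and short code blocks that mostly exist already, with no new data. The downside is that the rank test's p-value does not correspond to the reported odds ratio, which the text should say.

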##### 15.4.4.4 *Subject rating of change in neuropathic pain severity since study treatment start as measured by the PGIC-PS at Month 6*

The same approach (CMH test) as described in Section 15.2.5.1 will be used to analyze on the mFAS each of the 3 response variables defined in Section 9.6.4.

##### 15.4.4.5 *Change from baseline to Month 6 in the subject's rating of disease severity as measured by the PGIS-D*

The same approach (CMH test) as described in Section 15.2.5.1 will be used to analyze on the mFAS the proportion of subjects experiencing improvement.

**15.4.4.6 Subject rating of change in disease severity since study treatment start as measured by the PGIC-DS at Month 6**

The same approach (CMH test) as described in Section 15.2.5.1 will be used to analyze on the mFAS each of the 3 response variables defined in Section 9.6.6.

**15.4.4.7 Change from baseline to Month 6 in the total score of the subject's rating of the CESD-R-20**

The same approach (ANCOVA) as described in Section 15.4.2 will be used to analyze this endpoint on the mFAS.

The change from baseline to Month 6 in risk of depression will be compared between treatment groups using the CMH test stratified by sex and ERT treatment status at screening (treated vs not treated) at the two-sided significance level of  $\alpha = 0.05$ .

Due to the ordinal nature of the change in risk, modified ridit scores will be used to obtain the Van Elteren extension of the Wilcoxon rank-sum test. This analysis will be implemented by the following SAS® code:

```
proc freq;  
  tables sex*ertstatus*treatment*riskchange / nocol nopercnt scores=modridit cmh2;  
run;
```

The change from baseline to Month 6 in risk of depression will be further detailed within each treatment group by a shift table of the 5-level classification.

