#### **9.6.7 Change from baseline to Month 6 in the total score of the subject’s rating of the CESD-R-20**

Using the data collected at baseline and Month 6, the total score at baseline and the total score at Month 6 will be derived as the sum of the 20 questions. In order to make the revised

CESD-R have the same range as the original version (i.e., the ‘CESD style score’), the values for the top two responses are given the same value (i.e., answers with the value 4 are given the value 3). As in the original CESD, the range of possible scores is between 0 and 60.

The values collected during the study will be mapped to protocol visits according to the windowed times described in [Table 5](#).

If one question or more is unanswered the total score will be missing. The change from baseline to Month 6 will be calculated as the difference (total score at Month 6 – total score at baseline).

Since a total score  $\geq 16$  indicates a person at risk of clinical depression, a variable for change in risk of depression between baseline and Month 6 will be defined as decreased risk (at risk at baseline, not at risk at Month 6), no change (at risk at baseline and Month 6 or not at risk at baseline and Month 6), increased risk (not at risk at baseline, at risk at Month 6).

In addition to the binary classification of the total score ( $<16$ ,  $\geq 16$ ), the 5-level classification will also be derived [[Radloff 1977](#)]:

- Meets criteria for major depressive episode: anhedonia or dysphoria nearly every day for the past two weeks (defined as at least 1 question out of 2, 4, 6, 8 and 10 answered “nearly every day for 2 weeks”), plus symptoms in an additional 4 DSM symptom groups noted as occurring nearly every day for the past two weeks (defined as at least 1 question answered “nearly every day for 2 weeks” in at least 4 additional symptom groups);
- Probable major depressive episode: anhedonia or dysphoria nearly every day for the past two weeks (defined as above), plus symptoms in an additional 3 DSM symptom groups reported as occurring either nearly every day for the past two weeks, or 5–7 days in the past week (defined as at least 1 question answered “5–7 days” or “nearly every day for 2 weeks” in at least 3 additional symptom groups) without meeting the criteria for major depressive episode;

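### The change-in-depression-risk test leaves out baseline risk status, so it gives up some power and is exposed to chance baseline imbalance (minor)

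*SAP*

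**What the plan says.** SAP 9.6.7 takes a CESD-R-20 total of 16 or more as being at risk of clinical depression and builds a three-level change variable:

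- 'decreased' means at or above the cut-off at the start and below it at the end;
- the middle level is worded as "no change (at risk at baseline and Month 6 or not at risk at baseline and Month 6");
- 'increased' means below the cut-off at the start and at or above it at the end.

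SAP 15.4.4.7 compares this variable between arms, "at the two-sided significance level of" 0.05, with the Van Elteren form of the Cochran-Mantel-Haenszel test. On the strata it says that the shift "in risk of depression will be compared between treatment groups using the CMH test stratified by sex and ERT treatment status at screening". The code matches the text: "tables sex*ertstatus*treatment*riskchange / nocol nopercnt scores=modridit cmh2". Neither contains a term for baseline risk.

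The same section covers the total score separately: "The same approach (ANCOVA) as described in Section 15.4.2 will be used to analyze this endpoint on the mFAS". The Section 15.4.2 model has the baseline value as a covariate. Section 15.4.4.7 also plans a shift table of the five-level depression classification within each arm.

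**The concern.** Baseline status fixes the possible outcomes. A subject at risk at baseline can only be 'decreased' or 'no change'. A subject not at risk can only be 'no change' or 'increased'. 'No change' is therefore the worst result for the first group and the best for the second, yet both receive the same rank score.

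Two things follow. Variation in baseline status enters the comparison as noise. If the arms differ by chance in the proportion at risk at baseline, the test leans towards the arm with more at-risk subjects, because only they can improve. Randomization is not stratified by depression status, and placebo has only about 39 subjects.

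The SAP adjusts for baseline elsewhere: in the ANCOVA of the CESD-R-20 total score, and in the rank analysis of stool days (15.3.2), which regresses ranked change on ranked baseline before the CMH step. This is the only planned between-arm test of crossing the at-risk threshold.

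**Working it through.** **Inputs from the documents.** 118 randomized 2:1, about 79 and 39 (SAP 2); cut-off 16 (SAP 9.6.7); strata, scores and alpha (SAP 15.4.4.7).

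**Inputs that had to be assumed.** At-risk prevalence, stability of the score and drug effect. The documents give none of these and state no power for this test. The nearest stated figure is the primary endpoint's 87.2% (Protocol 10.5). It reproduces: noncentrality = 2 / (3 × √(1/66 + 1/33)) = 3.13, and the two-sided t-test power is 87.2%.

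**Step 1, how much of the variation is baseline status.** Code the outcome −1, 0, +1. Let p be the proportion at risk at baseline, a the chance of losing risk if at risk, and o the chance of onset if not.

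- Mean change = (1 − p)o − pa.
- Variance = [pa(1 − a) + (1 − p)o(1 − o)] + p(1 − p)(a + o)².

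The last term comes purely from baseline status. As an illustration, take a normal score with mean 16, so p = 0.5, and baseline to Month 6 correlation 0.5. Then a = o = arccos(0.5)/π = 1/3. The bracket is 0.222 and the baseline term is 0.25 × (2/3)² = 0.111, one third of the total of 0.333. With correlation 0.7, a = o = 0.253; the terms are 0.189 and 0.064, so the share is one quarter. Stratifying by baseline risk removes this part.

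**Step 2, chance imbalance.** With no drug effect, the arms' expected means differ by −(p_L − p_P)(a + o), where p_L and p_P are the proportions at risk in the lucerastat and placebo arms. For 50% against 35% at risk this is −0.15 × 2/3 = −0.10, in favour of lucerastat. Such an imbalance is 0.15 / √(0.45 × 0.55 × (1/79 + 1/39)) = 1.5 standard errors. Simulated under that condition, the planned test rejected in about 8 to 9% of trials, nearly all favouring lucerastat, against about 5% with the extra stratum. With the imbalance reversed (40% against 55%) it rejected in about 7%, nearly all favouring placebo.

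**Step 3, power.** Simulation of the planned test (4 strata) and of the same test with baseline risk added (8 strata): 79 and 39 subjects, latent score SD 12. Means of 12, 16 and 20 put Φ((mean − 16)/12) = 37%, 50% and 63% at risk; correlations were 0.5 and 0.7. The gain column covers runs with and without 15% missing data.

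| True effect | In SD units | Gain from the stratum |
|---|---|---|
| 0 | 0 | none; both tests about 5% |
| 3 points | 3/12 = 0.25 | about 3 to 7 percentage points |
| 5 points | 5/12 = 0.42 | about 6 to 16 |
| 7 points | 7/12 = 0.58 | about 10 to 24 |

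For scale, in runs without missing data power was 25 to 36% as planned and 38 to 46% with the stratum for 5 points, and 39 to 62% and 62 to 73% for 7 points. With transition rates set directly, an effect only in the at-risk group gave a gain of 3 to 10 percentage points, and an effect only in those not at risk gave 2 to 7. The gain was positive in every non-null setting.

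**The case against.** The strongest reply is that little depends on this test. The protocol endpoint is change in the total score (Protocol 6.1.4.4). The risk-change variable is added by the SAP, lies outside the fixed sequence, and belongs among the endpoints that SAP Table 2 calls exploratory. The ANCOVA of the total score adjusts for baseline and is far stronger: in the same kind of simulation it had 59 to 83% power for a 5-point effect and 87 to 98% for 7 points, against 36 to 46% and 58 to 74% for the amended risk test. This stands, and it is why the point is minor. A reader might infer that the depression objective lacks a sound baseline-adjusted analysis; the documents do not support that.

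A reader might also take the 8 to 9% rejection rate as inflated type I error. It is not. It is conditional on an imbalance chosen in advance. Over all randomizations the test holds its level, and any test that omits a prognostic baseline factor behaves in this way.

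The five-level shift table shows much of the movement by baseline state, so that information is partly there. It is descriptive, though, and does not collapse exactly to the cut-off: five items scored 3 can meet the top category with a total of 15.

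Finally, eight strata are thin: 39/8 is about 5 placebo subjects each if strata were equal. There will be fewer after missing data, since SAP 9.6.7 says "If one question or more is unanswered the total score will be missing". A stratum lacking one arm contributes nothing. This is a real cost, but it did not remove the gain with 15% missing.

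**Conclusion.** The point holds as a minor one. The test omits a baseline status that the trial already collects and that determines each subject's possible outcomes, and 'no change' carries two opposite meanings. The result is a valid exploratory test with less power than it could have, and a result that depends on chance baseline balance.

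The size is conditional on assumed inputs: about 3 to 7 percentage points of power for a 3-point effect, 6 to 16 for 5 points, 10 to 24 for 7 points, and as little as 2 if only one baseline group responds. A reader might want one figure for the loss. The documents cannot supply it, because they state no distribution, prevalence or effect, and a range taken only from moderate to large effects would overstate the lower end. No primary or secondary conclusion is affected.

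**What to change.** In SAP 15.4.4.7, add baseline risk status (total score below 16 against 16 or more) to the strata, in the text and in the code: `tables sex*ertstatus*baserisk*treatment*riskchange / scores=modridit cmh2`. The test then compares loss of risk among subjects at risk at baseline and onset of risk among those not at risk, and combines the two. Report both rates by arm with their denominators, so that 'no change' can be read.

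The cost is one variable in the TABLES statement and two rows in a table. Every subject with a defined change already has the baseline status. The number of strata rises from 4 to 8. If that is judged too thin, stratifying by baseline risk alone gave about the same or slightly more power in simulation. The choice should be fixed before unblinding.
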